#### **6.1.5                    Serious Adverse Event Reporting**

In the event of a serious adverse event, whether associated with study drug or not, the Investigator/designee will notify the Medical Monitor within 24 hours of the site being made aware of the serious adverse event by submitting the available serious adverse event data to:

#### **6.1.6                    Pregnancy**

Female subjects randomized or assigned to non-RBV containing regimen in Main study or Retreatment sub-study should avoid pregnancy starting with screening and through 30 days after completion of study drug. Female subjects randomized or assigned to RBV containing regimen in Main study or Retreatment sub-study should avoid pregnancy starting with Screening and through 6 months after completion of study drug (or as per

local RBV label). Male subjects randomized to G/P in Main study or receiving G/P plus SOF in Retreatment sub-study and their partners should avoid pregnancy starting with screening and through 30 days after completion of study drug. Male subjects randomized or assigned to RBV containing regimen in Main study or Retreatment sub-study and their partners should avoid pregnancy starting with Screening and through 7 months after completion of study drug (or as per local RBV label).

Pregnancy in a study subject must be reported to the sponsor within 1 working day of the site becoming aware of the pregnancy and should be reported to the Ribavirin Pregnancy Registry, as applicable. Administration of G/P in Main study or G/P plus SOF in Retreatment sub-study may be continued at the investigator's discretion after discussion with the subject, if the benefit of continuing therapy is felt to outweigh the risk (Section 5.4.1). If a subject is discontinued, the subject will be monitored for SVR in the Post-Treatment Period as described in Section 5.1.3.

Information regarding a pregnancy occurrence in a study subject and the outcome of the pregnancy will be collected for pregnancies occurring up to 30 days after the end of treatment for subjects receiving a non-RBV containing regimen or up to 6 months (female subjects) or 7 months (male subjects) after the end of treatment for subjects receiving a RBV containing regimen.

Pregnancy in a study subject is not considered an adverse event. However, the medical outcome of an elective or spontaneous abortion, stillbirth or congenital anomaly is considered a serious adverse event and must be reported to the sponsor within 24 hours of the site becoming aware of the event.

### **6.1.7                   Toxicity Management**

For the purpose of medical management, all adverse events and laboratory abnormalities that occur during the Main study or Retreatment sub-study must be evaluated by the

investigator/clinician designee. All adverse events and laboratory abnormalities will be managed and followed to a satisfactory clinical resolution.

To facilitate this process in a pragmatic study, after adverse event data is abstracted from the submitted records, the site investigator/clinician designee will be provided an adverse event listing to assess relationship of the adverse event to study drug(s). The site will also upload signed central lab reports where the investigator/clinician designee completed the evaluation of clinical significance of abnormal results. Actions taken for clinically significant abnormal laboratory results and/or adverse events will be recorded in the site medical record or source and uploaded for centralized abstraction.

## **6.2. Product Complaint**

### **6.2.1. Definition**

A Product Complaint is any Complaint (see Section 6.0 for the definition) related to the study drug product(s).

For a product this may include, but is not limited to, damaged/broken product or packaging, product appearance whose color/markings do not match the labelling, labelling discrepancies/inadequacies in the labelling/instructions (example: printing illegible), missing components/product, or packaging issues. Any product complaints identified centrally in the submitted medical records will be abstracted into the study database.

### **6.2.2. Reporting**

Product Complaints concerning the investigational product must be reported to the sponsor within 24 hours of the time it is observed or the data is abstracted centrally from the submitted medical records via the Product Complaint form. Product Complaints occurring during the study will be followed-up to a satisfactory conclusion via specific

query to the site for any available clinical information. All follow-up information is to be reported to the sponsor and documented in the source medical record. Product Complaints associated with adverse events will be reported in the study summary. All other complaints will be monitored on an ongoing basis.

Product Complaints may require return of the product with the alleged complaint condition. In instances where a return is requested, every effort should be made by the investigator/site to return the product within 30 days. If returns cannot be accommodated within 30 days, the site will need to provide justification and an estimated date of return.

The description of the complaint is important for AbbVie in order to enable AbbVie to investigate and determine if any corrective actions are required.

## 7.0 Protocol Deviations

The investigator should not implement any deviation from the protocol without prior review and agreement by the Sponsor and in accordance with the Independent Ethics Committee (IEC)/Independent Review Board (IRB) and local regulations, except when necessary to eliminate an immediate hazard to study subjects. When a deviation from the protocol is deemed necessary for an individual subject, the investigator must contact the following personnel:

If by e-mail: [REDACTED]

If by phone: [REDACTED] [REDACTED] (alternate contact)

Office: [REDACTED] Office: [REDACTED]

Such contact must be made as soon as possible to permit a review by the sponsor to determine the impact of the deviation on the subject and/or the study. Any significant protocol deviations affecting subject eligibility and/or safety must be reviewed and/or approved by the IEC/IRB and regulatory authorities, as applicable, prior to implementation.

## **8.0 Statistical Methods and Determination of Sample Size**

### **8.1 Statistical and Analytical Plans**

The primary analysis will occur after all subjects in the Main Study have completed the PT Week 12 Visit or prematurely discontinued study. The data for subjects treated in the Main study will be locked after data cleaning. Data from the Retreatment sub-study will be analyzed separately as described below and be included in the end-of study analysis.

The data analysis will be generated using SAS/STAT software, version 9.4 or higher of the SAS system for Windows. Copyright © [2001-2012] SAS Institute Inc. SAS and all other SAS Institute Inc. product or service names are registered trademarks or trademarks of SAS Institute Inc., Cary, NC, USA. All statistical tests (if applicable) and confidence intervals will be two-sided with an alpha level of 0.05. Descriptive statistics will be provided, such as the number of observations (N), mean, and standard deviation (SD) for continuous variables and counts and percentages for discrete variables.

The primary efficacy analyses in the Main study will be performed on the intention to treat population summarized according to the treatment arm in which the subject actually received treatment. This primary efficacy analysis dataset will be referred to as the modified ITT (mITT) population and defined as all enrolled subjects who receive at least one dose of study drug according to each subject's final treatment arm assignment (Arm A, Arm B, Arm C or Arm D). Analyses in the Retreatment sub-study will be performed overall on the Evaluable Patient population for that sub-study (EP-RS) defined as all subjects who receive at least one dose of study drug in the Retreatment sub-study.

The traditional ITT population, which includes all subjects who received at least one dose of study drug categorized by the patients' randomized treatment arm, along with other modified ITT populations will be employed in the sensitivity analyses. Specifically, sensitivity analyses of the primary endpoint of the Main Study will be performed on the following modified ITT populations:

- 1) Modified ITT-Genotype (mITT-GT) Population
  - includes the mITT population (or “as treated”) but excludes subjects with genotype other than GT1 infection.
- 2) Modified ITT- Genotype and Virologic Failure (mITT- GT-VF) Population
  - includes the mITT-GT population but excludes subjects who did not achieve SVR12 for reasons other than virologic failure (mITT-GT-VF), when applicable.

Similarly, for the Retreatment sub-study, sensitivity analyses of the SVR12 endpoint will be performed on the EP-RS population modified to exclude subjects other than GT1 (EP-RS-GT) and further modified to exclude subjects who did not achieve SVR12 for reasons other than virologic failure (EP-RS-GT-VF).

No data will be imputed for any efficacy or safety analysis except for analyses of SVR endpoints (HCV RNA data). HCV RNA values will be selected for the analyses of all SVR endpoints (e.g., SVR4 and SVR12) based on defined visit windows. A backward imputation method will be used to impute missing responses for SVR analyses.

Additional details of analyses to be performed are specified in the Statistical Analysis Plan.

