**Statistical Methods:**

The mITT population for the Main Study will be all subjects enrolled in the Main Study receiving at least one dose of study drug categorized according to the treatment arm in which they were actually treated, and the Evaluable Patient Population for the Retreatment sub-study (EP-RS) will be all subjects who receive at least one dose of G/P and of SOF in the Retreatment sub-study.

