MAGELLAN-1 enrolled a total of 11 NS5A inhibitor -experienced, PI-naïve subjects with compensated cirrhosis; 85.7% (6/7) and 75.5% (3/4) subjects achieved SVR12 with G/P 300 mg/120 mg for 12 or 16 weeks, respectively. The two subjects that did not achieve SVR12 experienced on-treatment virologic failure and may benefit from the addition of RBV which has

been shown to decrease the risk of both on-treatment failure and relapse. Therefore, the present study will evaluate G/P for 16 weeks and G/P + RBV for 12 weeks in NS5A inhibitor -experienced, PI-naïve subjects with compensated cirrhosis.

The objective of this study is therefore to obtain additional data with G/P in NS5A inhibitor-experienced, PI-naïve GT1-infected subjects that will help to optimize the G/P regimen for this population. The initial study design did not exclude patients with historical PI exposure prior to the NS5A-inbitor exposure as PI resistance has been shown to quickly revert to wild types, but did exclude only those who received a PI in combination with a NS5a. Since the initial study launch, G/P has been approved by the FDA and was given a label for NS5A experienced, PI naïve patients only; with 16 weeks of therapy. Thus, to minimize treatment failure in this population and more accurately reflect FDA label duration, patients with any prior PI exposure will be excluded from further recruitment into the study and any patient already enrolled or randomized to a 12-week arm will have their treatment extended to 16 weeks duration.

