##### **Treatment Arm Efficacy Adjustment Criteria**

Based on interim virologic data, the following adjustments will be made to individual treatment arms within the Main Study. Treatment Arm Efficacy Adjustment Criteria do not apply to the Retreatment sub-study:

1. If more than 2 subjects have confirmed on-treatment virologic failure among the first 20 non-cirrhotic subjects with available HCV viral load data across Arms A and B, the virologic failures will be examined to determine if all new enrollment into the arms should stop and if weight-based twice daily RBV (1000 mg  $<$  75 kg or 1200 mg  $\geq$  75 kg body weight total daily dose) should be added to the regimen for all future and current subjects in Arm A and Arm B, or a subset of subjects in Arms A and B. Similar analyses will continue every two weeks until all subjects in Arms A and B reach the end of treatment.
2. If more than 2 subjects have confirmed post-treatment relapse in the Post-Treatment

period among the first 20 subjects in Arm A with available post treatment HCV viral load data, the virologic failures will be examined to determine if treatment should be extended to 16 weeks for all future and current subjects in Arm A or for a subset of subjects in Arm A. Similar analyses will continue every two weeks until all subjects in Arm A reach the end of treatment.

3. If more than 2 subjects have confirmed post-treatment relapse among the first 20 subjects in Arm C with available post treatment HCV viral load data, the virologic failures will be examined to determine if treatment should be extended to 16 weeks for all future and current subjects ongoing in Arm C or for a subset of subjects in Arm C. Similar analyses will continue every two weeks until all subjects in Arm C reach the end of treatment.
4. If more than 2 subjects have confirmed on-treatment virologic failure among the first 20 subjects across Arms A, B and D, the virologic failures will be examined to determine if weight-based twice daily RBV (1000 mg <75 kg or 1200 mg  $\geq$ 75 kg body weight total daily dose) should be added for all current and future patients in Arm D or a subset of subjects in Arm D. Similar analyses will continue every two weeks until all subjects in Arms A, B and D reach the end of treatment.

Treatment failures due to non-compliance with study drugs, stopping or holding of study drugs due to adverse events, or other reasons for study drug interruptions will not count towards virologic failures.

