### **8.1.2.3 Sensitivity Analysis**

As sensitivity analyses, the difference in the percentage of subjects in the mITT-GT and mITT-GT-VF populations achieving SVR12 between Arm A and Arm B in non-cirrhotic subjects, and between Arm C and Arm D in cirrhotic subjects, as applicable, will be summarized. The SVR12 rates in the EP-RS-GT and EP-RS-GT-VF populations overall will be calculated.

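### The primary efficacy analysis groups subjects by treatment received, while the protocol moves PI-experienced subjects from 12 to 16 weeks, so the primary difference is confounded by prior PI exposure

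*Protocol*

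**What the plan says.** The Synopsis (Statistical Methods) and Section 8.1 define the primary set, mITT, by treatment received. In the Synopsis subjects are "categorized according to the treatment arm in which they were actually treated". In Section 8.1 the primary analyses are "summarized according to the treatment arm in which the subject actually received treatment", and the set comprises enrolled subjects "who receive at least one dose of study drug according to each subject's final treatment arm assignment".

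Two provisions can change duration after randomisation:

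- **Section 3.4.** The initial design admitted some subjects with earlier PI exposure. After the label was granted for PI-naive patients only, such subjects are no longer recruited, and "any patient already enrolled or randomized to a 12-week arm will have their treatment extended to 16 weeks duration". The reasons given are to limit failure in this group and to follow the label duration.
- **Section 5.4.1.1, Treatment Arm Efficacy Adjustment Criteria.** More than 2 confirmed relapses among the first 20 Arm A subjects with post-treatment data lead to a review of whether treatment should be "extended to 16 weeks for all future and current subjects in Arm A or for a subset of subjects in Arm A". Arm C has a parallel rule. Criteria 1 and 4 and Section 5.5.5 allow ribavirin (RBV) to be added in Arms A, B or D.

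Section 8.1 also defines a set "categorized by the patients' randomized treatment arm" and assigns it to the sensitivity analyses. The list that follows there names only mITT-GT and mITT-GT-VF. Section 8.1.2.3 likewise describes, for the Main study, "the difference in the percentage of subjects in the mITT-GT and mITT-GT-VF populations achieving" SVR12. Both of those sets are subsets of mITT and keep its as-treated grouping.

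**The concern.** Randomisation protects the comparison of A with B only if subjects are counted where they were randomised. Here the protocol itself moves a group defined by a baseline characteristic that it treats as raising the risk of failure, and the primary analysis then follows the move. Arm A loses the PI-experienced subjects who are extended. The 16-week group keeps its own and gains those from Arm A. The same applies to C against D, and to the pooled secondary comparison of 12 with 16 weeks.

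The primary difference then mixes the effect of duration with the effect of PI exposure. The confidence interval does not reflect this, and a larger sample would not reduce it.

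The definition also fails for some subjects. An Arm C subject extended to 16 weeks of G/P plus RBV matches neither Arm C (12 weeks with RBV) nor Arm D (16 weeks without RBV). A subject in Arm A, B or D with RBV added matches no defined arm either.

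**Working it through.** **The plan's own precision figure.** Section 8.2 assumes 100 subjects in Arm A and 50 in Arm B. The half-width is 1.96 × √[p_A(1−p_A)/100 + p_B(1−p_B)/50]. At 92% in both arms this gives 0.092, and at 96% it gives 0.067, as tabulated. The A versus B table therefore spans roughly 7 to 9 points, for 12-week deficits of 0, 1 and 2 points.

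**Failure rates from the protocol.**

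- PI-naive, NS5A-experienced GT1 subjects on G/P without RBV (Section 3.4): SVR12 18/20 + 17/18 = 35/38, so f0 = 3/38 = 7.9%.
- GT1 subjects with prior NS5A inhibitor and/or PI (Section 3.1.1, Table 2): 97/109. If the 38 lie within the 109, the remainder is 62/71, so f1 = 9/71 = 12.7%.
- Difference f1 − f0 = 4.8 points. The Wilson 95% interval for 62/71 is 78% to 93%, and Fisher's exact test of 9/71 against 3/38 gives p = 0.54.

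**Bias formula.** Let k of the 150 non-cirrhotic subjects be PI-experienced, split 2:1, with no true effect of duration and every Arm A case extended. As treated, Arm A fails at rate f0. Arm B has n_B = 50 + 2k/3 subjects and (50 − k/3)f0 + k·f1 expected failures. The bias in SVR12, A minus B, is therefore k(f1 − f0)/n_B. By randomised arm the expected difference is 0. The protocol does not give k, so 5 to 20 is assumed.

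| k (assumed) | n_B | Bias, 12.7% vs 7.9% | Bias, assumed 20% vs 5% | Bias, assumed 30% vs 5% |
|---|---|---|---|---|
| 5 | 53.3 | +0.4 | +1.4 | +2.3 |
| 10 | 56.7 | +0.8 | +2.6 | +4.4 |
| 20 | 63.3 | +1.5 | +4.7 | +7.9 |

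Only the third column uses rates derived from the protocol. Replacing 35/38 by the 94.4% planning rate of Section 8.2 widens the gap to 12.7 − 5.6 = 7.1 points and the bias to +0.7 (k = 5) to +2.2 (k = 20). That is less like for like, because 94.4% is a 16-week rate and the 71 include both durations.

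**Subjects who had already finished 12 weeks.** If half of Arm A's PI-experienced subjects could no longer be extended, the bias is [(2k/3)/(50 + k/3) − (k/3)/(100 − k/3)] × (f1 − f0), which is +0.2 (k = 5) to +0.8 (k = 20). If all had finished, it is 0.

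**Effect on a real deficit.** Suppose 12 weeks is truly 2 points worse in PI-naive subjects and all PI-experienced subjects receive 16 weeks. With k = 20:

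- as treated: −2.0 + 1.5 = −0.5 points;
- by randomised arm, all dosed subjects: −2.0 × 130/150 = −1.7 points;
- by randomised arm, PI-naive subjects only: −2.0 points.

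**Relapse-triggered extension.** At a true relapse rate of 5% or 10%, the chance of more than 2 relapses in the first 20 is 7.6% or 32%. Given a trigger, the relapse rate observed in those 20 averages 16% to 18%. They have finished 12 weeks and stay in the 12-week arm.

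**The case against.** - **Weak rates.** The 9/71 comes from subtraction, mixes PI-only with other exposure and all cirrhosis statuses, and is not clearly different from 3/38. Section 3.4 says the initial design excluded subjects given a PI together with an NS5A inhibitor, and that PI resistance quickly reverts. The 71 are therefore not the subjects enrolled here. This stands: it limits the size, and the direction is conditional on PI-experienced subjects failing more often.
- **Not everyone moves.** A reader might infer that Arm A loses all its PI-experienced subjects. The protocol does not say so; those who had completed 12 weeks stay in Arm A. This stands.
- **Relapse-triggered moves.** A reader might infer that these also favour 12 weeks. They depend on a review, and the relapsers who set off the trigger remain in the 12-week arm. If extension is unselective the bias may run against 12 weeks; a bias in favour needs a high-risk subset to be moved. This stands.
- **No decision rule.** There is no margin or hypothesis, only a difference with its interval. It would therefore be too strong to say that the bias leads the trial to declare 12 weeks adequate. The estimate is still the primary result.
- **Already covered.** Section 8.1 does assign the by-randomised-arm set to sensitivity analyses, and Section 8.1.2.4 plans subgroups by all prior HCV treatment. So the randomised comparison is demoted, not absent. That does not repair the primary estimate, and the subgroup analysis is uninformative if as-treated Arm A holds few PI-experienced subjects.
- **ITT dilutes.** Counting extended subjects in Arm A shrinks a true effect of duration (−1.7 for −2.0 above). This is correct, and is why the fix also restricts to PI-naive subjects.

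**Conclusion.** The concern holds in limited form. The primary comparison follows treatment received, while the protocol changes duration after randomisation on a baseline factor it regards as prognostic. On rates derived from the protocol the bias is between 0 and about +1.5 points in favour of 12 weeks, assuming at most 20 PI-experienced non-cirrhotic subjects and a higher failure rate among them. Values up to +7.9 points need failure rates that the protocol does not supply. The bias is small against the 7 to 9 point half-width, but of the same order as the 1 to 2 point deficits the plan tabulates.

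The direction claim covers the PI-related extension only. Relapse-triggered changes would break the randomised grouping if used, with uncertain direction. Separately, the final arm is undefined for an extended Arm C subject and for subjects with RBV added in Arms A, B or D. The Synopsis arm definitions and Sections 5.4.1.1, 5.5.5 and 8.1 must be reconciled on this.

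**What to change.** 1. Make the primary comparison by randomised arm among dosed subjects, restricted to PI-naive subjects in both arms of each pair. PI exposure is a baseline fact, so the restriction is symmetric, and it matches the target population in Section 3.4.
2. Keep two sensitivity analyses: the as-treated mITT set, and all dosed subjects by randomised arm. Name the latter in Section 8.1.2.3.
3. If an adjustment criterion changes an arm's regimen, add a sensitivity comparison limited to subjects concurrently randomised before the change.
4. State, for as-treated summaries, how subjects on a regimen that matches no defined arm are classified.

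The cost is wording and one programming flag; no subject's treatment changes. The PI-experienced subjects leave the primary set and intervals widen slightly. At 94% in both arms, by the formula of Section 8.2, the half-width goes from 8.1 points with 150 subjects to 8.2 with 145 (1.96 × √[0.0564 × (1/96.7 + 1/48.3)]) or 8.7 with 130 (1.96 × √[0.0564 × (1/86.7 + 1/43.3)]).

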**Efficacy:**

The primary efficacy endpoints for the mITT population are the difference in SVR12 (HCV RNA < LLOQ 12 weeks after the last actual dose of study drug) rates between Arm A and Arm B in non-cirrhotic subjects, and difference in SVR12 rates between Arm C and Arm D in cirrhotic subjects.

The difference in SVR12 rates will be summarized with a two-sided 95% confidence interval for the comparison between Arm A and Arm B in non-cirrhotic subjects, and for the comparison between Arm C and Arm D in cirrhotic subjects. The number and percentage of subjects achieving SVR12 by treatment arm according to final treatment arm assignment of subjects will also be summarized with a two-sided 95% confidence interval. The confidence interval for the difference in SVR12 rates will be calculated using Wilson's score method. The confidence interval for the SVR12 rates by treatment arm will be calculated using the normal approximation to the binomial distribution if the number of subjects who failed to achieve SVR12 is at least 5. If the number of subjects who failed to achieve SVR12 is less than 5, Wilson's score method will be used instead.

The secondary efficacy variables are:

1. The difference in SVR12 rates between G/P given for 12 weeks (Arm A and C combined) and G/P given for 16 weeks (Arm B and D combined);
2. The percentage of subjects with on-treatment virologic failure;
3. The percentage of subjects with post-treatment relapse.

For the Main study, the differences in the percentages of subjects with on-treatment virologic failure or post-treatment relapse for non-cirrhotic subjects (Arm A vs Arm B) and subjects with compensated cirrhosis (Arm C vs Arm D) will be summarized along with 95% Wilson score intervals. Additional efficacy endpoints and efficacy subgroup analyses will be performed.

As an additional efficacy endpoint, the percentage of retreated subjects achieving SVR12 will be analysed on the EP-RS population overall for the Retreatment sub-study.

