### **Definition of Terms**

Study Drug	Glecaprevir (ABT-493), pibrentasvir (ABT-530), Ribavirin (RBV), *Sofosbuvir (GS-7977)
Study Day 1	First day of study drug dosing
Treatment Period	Day 1 through last dose of study drug
Post-Treatment Period	Day after the last dose of study drug through Post-Treatment Week 12 or Post-Treatment Discontinuation

Note: Differentiation between terms within the Main Study and Re-Treatment Substudy will be made with the use of headers throughout the protocol

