#### **5.3.2.1 Primary Variable**

The primary efficacy variable is SVR12 (HCV RNA < LLOQ 12 weeks after the last actual dose of study drug).

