### **5.5.5 Selection and Timing of Dose for Each Subject**

G/P is a fixed-dose combination tablet of 100 mg glecaprevir and 40 mg Pibrentasvir. The dose used for all subjects in this study is 300 mg/120 mg G/P, given together once daily with food. The maximum dose of G/P will not exceed 300 mg/120 mg per day for 16 weeks in the Main study and also in the Retreatment sub-study, if applicable.

For the Retreatment sub-study, SOF is provided as 400 mg tablets and should be taken simultaneously with G/P.

Ribavirin (RBV) (if applicable) is provided as 200 mg tablets\*\*\* and should be dosed BID, e.g., with 2 to 3 tablets\*\*\* taken in the morning, and 2 to 3 tablets\*\*\* taken in the evening based on body weight and must also be taken with food. For subjects with body

weight less than 75kg RBV is dosed at 1000 mg per day (e.g., 400 mg in AM and 600 mg in PM, or 600 mg in AM and 400 mg in PM). For subjects with body weight equal or greater than 75kg, RBV is dosed at 1200 mg per day (e.g., 600 mg in AM and 600 mg in PM). The maximal dose of RBV will not exceed 1200 mg per day for 16 weeks.

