#### **8.1.2.5 Additional Efficacy Endpoints**

The following additional efficacy endpoints will be summarized for each treatment arm in the mITT population and overall in the EP-RS population, as specified below:

- The percentage of mITT subjects with HCV RNA < LLOQ at each post-baseline visit in the Treatment Period (using data as observed);
- The percentage of mITT subjects with SVR4;
- The percentage of EP-RS subjects achieving SVR12.
- The percentage of EP-RS subjects with on-treatment virologic failure and with post-treatment relapse.

In the above analyses for SVR, the percentage of subjects and a two-sided 95% Wilson score interval will be summarized. A summary of reasons for SVR non-response will also be provided for subjects in the EP-RS populations who do not achieve SVR12.

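### The protocol gives the retreatment analysis population (EP-RS) two definitions, which disagree about a retreated subject who never takes SOF

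*Protocol*

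**What the plan says.** The synopsis, under Statistical Methods, defines EP-RS as "all subjects who receive at least one dose of G/P and of SOF in the Retreatment sub-study". Section 8.1 uses the same name for a population "defined as all subjects who receive at least one dose of study drug in the Retreatment sub-study". The Definition of Terms gives study drug as "Glecaprevir (ABT-493), pibrentasvir (ABT-530), Ribavirin (RBV), *Sofosbuvir (GS-7977"), with sofosbuvir marked as belonging to the sub-study. A dose of any one of these meets the Section 8.1 condition.

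The synopsis states that "the percentage of retreated subjects achieving SVR 12 will be analysed on the EP-RS population overall for the Retreatment sub-study". Section 8.1.2.5 adds on-treatment virologic failure, relapse and reasons for non-response in the same population, and gives the SVR format: "In the above analyses for SVR, the percentage of subjects and a two-sided 95% Wilson score interval will be summarized". Demographics, exposure and compliance (Section 8.1.1) and resistance (Section 8.1.3) also use EP-RS. The sensitivity sets EP-RS-GT and EP-RS-GT-VF are obtained by removing subjects from it (Section 8.1).

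On dosing, Section 5.5.5 says that "SOF is provided as 400 mg tablets and should be taken simultaneously with G/P".

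**The concern.** The protocol fixes one named analysis set twice, with different content, and does not say which text governs. This is more than a detail left for the SAP.

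The synopsis rule removes a subject who was dosed in the sub-study, on the basis of which drugs were actually taken. That can be related to outcome. The Section 8.1 rule keeps every dosed subject, in line with the one-dose rule for the Main Study mITT population (Section 8.1) and for the safety analyses (Section 8.1.4).

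At stake is the retreatment SVR12 rate and its interval. The sub-study can only be small, since it draws on virologic failures from a Main Study of at most 225 subjects, so one subject in or out of the denominator is visible in the result. The sub-study is also open-label, which is a reason to settle the denominator before the data are reviewed.

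**Working it through.** **Step 1. Compare the two rules.**

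| Retreated subject takes | Synopsis | Section 8.1 |
|---|---|---|
| G/P and SOF, with or without RBV | in | in |
| G/P at first, SOF started later | in | in |
| G/P, with or without RBV, never SOF | out | in |
| SOF, never G/P | out | in |
| RBV only | out | in |

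The synopsis sets no time by which SOF must start, so late SOF does not exclude anyone. The case of most interest is the third row.

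**Step 2. How that subject's outcome is decided.** Section 5.3.2.1: "The primary efficacy variable is SVR 12 (HCV RNA < LLOQ 12 weeks after the last actual dose of study drug"). Section 8.1: "A backward imputation method will be used to impute missing responses for SVR analyses". Neither refers to which drugs were taken. Under Section 8.1 the subject is in the denominator and HCV RNA decides whether the subject is a responder.

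**Step 3. Size.** The protocol gives no sample size or precision figure for the sub-study, so there is none to reproduce. The number dosed, n, is an assumption:

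- n = 7: the number of GT1 subjects in the cited retreatment study of G/P failures (Introduction, G/P+SOF+/-RBV for G/P treatment failures).
- n = 13: 225 × (1 − 0.944) = 12.6, using the 16-week rate in Section 8.2.
- n = 24: 225 × (1 − 0.894) = 23.8, using 101/113 = 89.4% from Table 2.

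The last two count every subject without SVR12. Only virologic failures who consent may enter. At the minimum enrolment of 175 the middle figure would be 175 × 0.056 = 9.8.

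Assume one of the n subjects never takes SOF, and let s be the number of responders among the other n − 1. Take s as 0.86 × (n − 1), rounded, from the 6/7 (86%) in the cited retreatment study.

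- Synopsis rate: s/(n − 1).
- Section 8.1 rate: s/n if that subject does not reach SVR12, or (s + 1)/n if SVR12 is reached.
- Fall if SVR12 is not reached: s/(n − 1) − s/n = s/[n(n − 1)].
- Rise if it is reached: (s + 1)/n − s/(n − 1) = (n − 1 − s)/[n(n − 1)].

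Intervals are two-sided 95% Wilson, [p + z²/2n ± z√(p(1 − p)/n + z²/4n²)]/(1 + z²/n), with z = 1.96.

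| n | Synopsis | 8.1, SVR12 not reached | 8.1, SVR12 reached |
|---|---|---|---|
| 7 | 5/6 = 83.3% (43.6–97.0) | 5/7 = 71.4% (35.9–91.8) | 6/7 = 85.7% (48.7–97.4) |
| 13 | 10/12 = 83.3% (55.2–95.3) | 10/13 = 76.9% (49.7–91.8) | 11/13 = 84.6% (57.8–95.7) |
| 24 | 20/23 = 87.0% (67.9–95.5) | 20/24 = 83.3% (64.1–93.3) | 21/24 = 87.5% (69.0–95.7) |

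Falls: 5/42 = 11.9 points, 10/156 = 6.4 points, 20/552 = 3.6 points.

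Rises: 1/42 = 2.4 points, 2/156 = 1.3 points, 3/552 = 0.5 points.

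**The case against.** The best defence is that the two definitions will probably select the same people. The SOF prescription must be in the upload that precedes treatment (Table 5, footnote j). Both suppliers ship to the study site after eligibility is verified (Section 5.5.4), the full regimen is dispensed there (Section 5.5.1.1), and SOF is to be taken with G/P (Sections 5.3.1.2 and 5.5.5). A subject with G/P and no SOF would be a deviation. This stands and limits the practical weight. It does not exclude the case, and the both-drugs condition has an effect only when such a case occurs.

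It can also be said that a both-drugs set is a reasonable evaluable population for a G/P plus SOF regimen, and that the Section 8.1 wording would admit a subject who took only RBV. Both are fair. They bear on which rule to choose, and the protocol still has to use one. The SAP, to which Section 8.1 refers for further detail, may already settle the matter. It was not available to check.

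Four stronger readings are tempting, and the documents do not support them:

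- That a never-SOF subject is automatically a failure under Section 8.1. HCV RNA decides (Step 2).
- That starting without SOF is enough to be dropped under the synopsis. One SOF dose at any time in the sub-study satisfies that rule.
- That such subjects are likely non-responders, so the synopsis rule always flatters. The protocol gives no outcome data for G/P without SOF in this retreatment setting, and the difference can go either way.
- That the denominator will be chosen after the results. Two definitions leave room for that, but nothing indicates it is intended.

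A sharper example is easy to build: 11 of 11 responders plus one never-SOF non-responder gives 100% against 11/12 = 91.7%. The arithmetic is right, but it assumes a perfect response in the others and a failure in the one subject, so it shows only one side.

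**Conclusion.** The contradiction is real: EP-RS has two definitions, and a retreated subject who never receives SOF is counted under one and excluded under the other. One such subject would put the Section 8.1 rate about 4 to 12 points below the synopsis rate if SVR12 is not reached, or 0.5 to 2.4 points above it if SVR12 is reached. These figures rest on an assumed 7 to 24 dosed subjects, about 86% SVR12 among the others, and exactly one discordant subject. With no such subject the difference is zero.

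The weight is low. Retreatment SVR12 is an additional, descriptive endpoint in a non-randomised sub-study, and no Main Study analysis changes. It is a minor point, worth correcting because the correction is cheap.

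**What to change.** Use one EP-RS definition in the synopsis and in Section 8.1. The Section 8.1 wording is preferable because it keeps every dosed subject and matches the Main Study mITT and safety rules. List any retreated subject who did not receive both G/P and SOF, with the HCV RNA outcome. Show the both-drugs set only as a sensitivity analysis. If the sponsor prefers the both-drugs rule as the main definition, Section 8.1 should say so and the dosed subjects it excludes should be listed.

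The cost is one sentence in the synopsis and a short listing. No additional data are needed. The reported retreatment SVR12 rate could be slightly less favourable if a never-SOF subject without SVR12 is retained.
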